7.7 Visit by visit events

7.7.1 Recruitment

Participants will contact the research team via email in response to the recruitment advertisements if they are interested in taking part in the study.

7.7.2 Screening visit

The following interventions and assessments will be completed in order at the screening visits:

- i. Informed consent
- ii. Collection of demographic information
- iii. Medical review and examination
- iv. Height, weight, body fat
- v. Review of eligibility
- vi. Urine sample for urinalysis, pregnancy and illicit drugs testing
- vii. Alcohol breath test
- viii. Blood sampling
- ix. Vital Signs
- x. Stool sampling kit provided to take home (optional)
- xi. Fasting instructions
- xii. Alert card and safety instructions

7.7.3 Experimental Visit

7.7.3.1 Day 1

The following interventions and assessments will be completed in order:

- i. Fasting (previous night from 10pm)
- ii. Eligibility review
- iii. Urine sample for pregnancy and illicit drugs testing

- iv. Alcohol breath test
- v. GSRS
- vi. Intravenous cannulation
- vii. Pre dose; 0-5mins: blood sampling; vital signs; DEQ-5
- viii. 0 mins: drug administration
- ix. 30mins: blood sampling
- x. 1 hour: blood sampling; vital signs; DEQ-5
- xi. 2 hours: blood sampling; vital signs; DEQ-5
- xii. 3 hours: blood sampling
- xiii. 4 hours: blood sampling; vital signs; DEQ-5; urinalysis
- xiv. 5 hours: blood sampling
- xv. 6 hours: blood sampling
- xvi. 8 hours: blood sampling; vital signs; DEQ-5; adverse events assessment

7.7.3.1 Day 2

- i. 24 hours post dose: blood sampling; vital signs; DEQ-5; GSRS; adverse events assessment

7.7.3.1 Day 3

- i. 48 hours post dose: blood sampling; vital signs; DEQ-5; GSRS; adverse events assessment.
- ii. Payment via bank transfer (if final visit)
- iii. Book follow-up visit (if final visit) and provide a urine pregnancy test (if female)

7.7.4 Washout

There will be a minimum 2 week washout between experimental visits.

7.7.5 Follow-up visit

The follow-up visit will be completed via remote video call 7-14 days after day 1 of experiment 2. Participants will be asked to report adverse events. Female participants of childbearing potential will be asked to confirm the result of a urine pregnancy test completed on that day.

7.8 Planned analyses

Blood samples will be analysed for CBD and its metabolites (including 6-OH-CBD, 7-OH-CBD, 7-COOH-CBD) CBDA, THC, endocannabinoids (including anandamide and 2-arachidonoylglycerol). Additional unplanned analyses of relevant metabolites, biomarkers or inflammatory markers may also be completed. The laboratory analyses will be completed at the University of Turku, Finland. Analyses will be completed once all samples have been collected, at the end of the study. All analyses will be completed in accordance with relevant guidance and legislation.

8. COVID-19

The study's COVID risk assessment highlighted no trial procedures which present risks beyond those which are encountered in routine clinical care (i.e. there are no vulnerable participants and no aerosol generating procedures). Therefore, standard King's College Hospital's guidance on the management of SARS-CoV-2 associated risks will be followed throughout the study. Vaccinations and vaccination status are not relevant to the trial or any of its procedures. If the CRF were to close due to any reason, follow-up and safety assessments will be completed at an appropriate NHS or KCL facility or online.

9. SAFETY

9.1 Definitions

The Medicines for Human Use (Clinical Trials) Regulations 2004 and Amended Regulations 2006 gives the following definitions:

- **Adverse Event (AE):** Any untoward medical occurrence in a participant to whom a medicinal product has been administered, including occurrences which are not necessarily caused by or related to that product.
- **Adverse Reaction (AR):** Any untoward and unintended response in a participant to an investigational medicinal product which is related to any dose administered to that participant.
- **Unexpected Adverse Reaction (UAR):** An adverse reaction the nature and severity of which is not consistent with the information about the medicinal product in question set out in the investigator's brochure for CBD.
- **Serious adverse Event (SAE), Serious Adverse Reaction (SAR) or Suspected Unexpected Serious Adverse Reaction (SUSAR):** Any adverse event, adverse reaction or unexpected adverse reaction, respectively, that:
 - results in death;
 - is life-threatening;
 - required hospitalisation or prolongation of existing hospitalisation;
 - results in persistent or significant disability or incapacity;
 - consists of a congenital anomaly or birth defect.
- **Important Medical Events (IME) & Pregnancy:** Events that may not be immediately life-threatening or result in death or hospitalisation but may jeopardise the participant or may require intervention to prevent one of the other outcomes listed in the definition above should also be considered serious. Although not a serious adverse event, any unplanned pregnancy will also be reported via the SAE reporting system.

9.2 Investigator Assessment

The investigator will seek information on adverse events from participants at 8 hours, 24 hours and 48 hours after each drug administration. Participants will also be able to spontaneously report adverse events throughout the lifetime of the trial. The investigator will use specific questioning and, as appropriate, examination. Information elicited will be recorded participant's Case Report Form. All

clearly related signs, symptoms, and abnormal diagnostic procedures will be recorded. The clinical course of each event should be followed until resolution or stabilisation.

9.3 Reporting Responsibilities

The sponsors have delegated the delivery of the Sponsor's responsibility for Pharmacovigilance (as defined in Regulation 5 of the Medicines for Human Use (Clinical Trials) Regulations 2004 to the King's Health Partners Clinical Trials Office (KHP-CTO).

All SAEs, SARs and SUSARs will be reported immediately (and certainly no later than 24hrs) by the Investigator to the KHP-CTO and CI for review in accordance with the current Pharmacovigilance Policy. The KHP-CTO will report SUSARs to the MHRA.

The Chief Investigator will report to the relevant ethics committee. Reporting timelines are as follows:

- SUSARs which are fatal or life-threatening must be reported not later than 7 days after the sponsor is first aware of the reaction. Any additional relevant information must be reported within a further 8 days;
- SUSARs that are not fatal or life-threatening must be reported within 15 days of the sponsor first becoming aware of the reaction.

The Chief Investigator and KHP-CTO (on behalf of the sponsor), will submit a Development Safety Update Report (DSUR) relating to this trial IMP, to the MHRA and REC annually.

King's College London will undertake all sponsor duties and pharmacovigilance. The Investigator is responsible for ensuring that all adverse events occurring during the study treatment period are recorded on Case Report Forms.

9.4 Premature Termination of the Trial

The trial may be prematurely discontinued by the Sponsor, Chief Investigator or Regulatory Authority on the basis of new safety information or for other reasons given by the trial's research team, regulatory authority or ethics committee concerned. If the trial is prematurely discontinued, active participants will be informed and no further participant data will be collected. The Competent Authority and Research Ethics Committee will be informed within 15 days of the early termination of the trial. There are no pre-specified treatment stopping rules.

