7.5.3 Adverse events

Participants will be asked to report adverse events at each blood sampling timepoint i.e. pre-dose (0-5mins), 0.5, 1, 2, 3, 4, 5, 6, 8, 24, 48hrs post-dose and at the 7-14 day follow-up visit. Participants will be asked specifically about adverse events including, but not limited to, anxiety, irritability, somnolence, dizziness, disorientation, nausea, abdominal pain, abdominal distension, diarrhoea, vomiting, and flatulence.

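### Protocol 9.4 halts all participant data collection on early termination with no exception for safety data, which conflicts with the safety follow-up and recording required in 9.2, 9.3 and, after the second dose, 7.5.3 and 7.7.5

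*Protocol*

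**What the plan says.** Protocol 9.4 lets the sponsor, chief investigator or regulator end the trial "on the basis of new safety information or for other reasons given by the trial's research team", among other grounds. It then says: "If the trial is prematurely discontinued, active participants will be informed and no further participant data will be collected". It also states that there are no pre-specified stopping rules.

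Other sections set safety duties that run past the moment of dosing:

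- Protocol 9.2: "The investigator will seek information on adverse events from participants at 8 hours, 24 hours and 48 hours after each drug administration". What is elicited goes in the Case Report Form. The section adds: "The clinical course of each event should be followed until resolution or stabilisation".
- Protocol 9.3: "The Investigator is responsible for ensuring that all adverse events occurring during the study treatment period are recorded on Case Report Forms". For a fatal or life-threatening SUSAR, further relevant information is due within 8 days after the 7-day report.
- Protocol 7.5.3, repeated in SAP 8.3: adverse events are asked about at each blood-sampling time "and at the 7-14 day follow-up visit".
- Protocol 7.7.5: "The follow-up visit will be completed via remote video call 7-14 days after day 1 of experiment 2". That call covers adverse events and, for women of childbearing potential, a pregnancy test result.

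The SAP has no rule for data arising after an early stop.

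**The concern.** A safety stop is the situation in which the outcome of the triggering event, and any delayed events in others recently dosed, are most needed. Section 9.4 is the only provision written for that situation, and it tells the site to stop collecting participant data. Sections 9.2 and 9.3 make adverse-event information Case Report Form content, so it falls within the plain meaning of participant data. Site staff could not obey 9.4 to the letter and also meet the other sections.

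At stake is the completeness of the safety record. The listings and the tables of treatment-emergent events in SAP 10.6.7 would stop at the termination date. Under SAP 10.4.3, an event that cannot be classed as resolved because its stop date is missing is taken to be ongoing. Open events would then carry an assumed status where an observed outcome was intended. The study has no data monitoring or steering committee (Protocol section 11), so investigator follow-up carries much of the safety oversight.

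**Working it through.** The plan gives no figure to reproduce on this point, so the check is mainly a comparison of texts.

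**Step 1. The 9.4 halt against each duty**

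| Duty | Who it covers | Effect of 9.4 read literally |
|---|---|---|
| Enquiry at 8, 24 and 48 h (9.2), with vital signs at those times (7.5.2) | Anyone dosed less than 48 h before termination, in either experiment | Remaining assessments not recorded |
| Following each event to its outcome (9.2) | Anyone with an open event | Outcome not recorded |
| Adverse events on Case Report Forms (9.3) | Anyone dosed | Later events not recorded there |
| Further SUSAR information within 8 more days (9.3) | Anyone with a fatal or life-threatening SUSAR | Report still due, but collecting its content is not provided for |
| 7-14 day follow-up (7.5.3, 7.7.5, SAP 8.3) | Only those already dosed in experiment 2 | Contact and pregnancy result lost |

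The last row is limited because the follow-up visit is timed from day 1 of experiment 2 in 7.7.5, in the flow chart (4.5) and in the synopsis. A participant dosed only in experiment 1 has no such visit scheduled. For that person the conflict is with 9.2 and 9.3.

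**Step 2. Is there an exemption elsewhere?**

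- Protocol section 8 keeps follow-up and safety assessments going, but only if the research facility closes.
- Protocol 6.11 defines the end of the trial as database lock. That does not restore collection that 9.4 has halted.
- Section 9.5 covers pausing the study and adjusting the dose, which is a different event from termination.
- SAP 8.3 and 10.4.3 say nothing about an early stop.

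Neither document contains an exemption.

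**Step 3. How many people would be affected (illustration)**

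Inputs: 14 participants with two doses each, and a planned trial duration of 4 months (synopsis). Assumption: dosing is spread evenly over the whole 4 months, which is 4 x 52.2 / 12 = 17.4 weeks.

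- Rate of second doses: 14 / 17.4 = 0.80 per week. First doses run at the same rate.
- Within 14 days of a second dose: 14 / 17.4 x 2 = 1.6.
- Within 48 h of a first dose: 0.80 x 2/7 = 0.2.
- Total: 1.6 + 0.2 = 1.8, or about 2 participants with scheduled safety follow-up outstanding.

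If every follow-up call took place at day 7 and not day 14, the first term would halve to 0.8 and the total would be about 1.0. If all dosing fell within half of the 4 months, the total would double to about 3.6. Participants with an unresolved event outside these windows would be additional, and the documents give no rate for them.

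**The case against.** The strongest reply is that 9.4 limits data collection and nothing else. It does not stop care or observation. Participants leave the facility only when clinical measures are normal, and they can contact the investigators at any time afterwards (Protocol section 3). Out-of-hours contact and emergency unblinding are provided (6.9). Spontaneous reports are accepted for the life of the trial (9.2), which ends at database lock (6.11). Expedited reporting under 9.3 has no exception for a stopped trial. The authors may have meant only that dosing and pharmacokinetic sampling would cease. A pause under 9.5 is also available and does not trigger the 9.4 sentence.

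Much of this stands, and it rules out several stronger conclusions that a reader might draw:

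- *That termination would end medical follow-up or SAE and SUSAR reporting.* The text does not say so. What ends, on a literal reading, is the recording of scheduled safety data and of event outcomes.
- *That everyone within 14 days of any dose would lose follow-up, so that 14 of 14 could be affected if all first doses were given within 5 days (14 / 3 = 4.7) at the permitted three sessions per day.* After a first dose, scheduled contact ends at 48 h until experiment 2. At that pace about 6 people would have assessments outstanding, and at most 9 (three dosing days x 3). All 14 could be awaiting follow-up only once second doses were complete, when little remains to terminate.
- *That the loss would bias the comparison of formulations.* Nothing in the documents shows that truncation would differ by formulation in this blinded crossover, and the tables of a terminated trial would be incomplete in any case.

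The reply does not remove the contradiction. If the authors intended a narrower halt, 9.4 does not say so, and nothing states that 9.2 or 9.3 takes precedence over it.

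**Conclusion.** The point holds as an internal contradiction. Section 9.4, which expressly covers a safety stop, halts all participant data collection. Sections 9.2 and 9.3 require continued safety enquiry, recording and follow-up of events for people already dosed. For those dosed in experiment 2, so do 7.5.3, 7.7.5 and SAP 8.3. Followed literally, 9.4 leaves a poorer safety record than the rest of the plan calls for.

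The effect arises only if the trial is terminated early. At an even dosing pace it would touch the scheduled follow-up of about 2 participants at a time, plus anyone else with an open event. That count rests on the even-pace assumption, and the finding does not depend on it. The consequence is incomplete adverse-event listings and tables. Sample size, power and the AUCinf analysis are unaffected.

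**What to change.** The sponsor should reconcile 9.4 with 9.2, 9.3, 7.5.3 and 7.7.5. One added sentence in 9.4 would do it, stating two things:

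- The halt on data collection does not apply to the safety data that the protocol already requires from participants already dosed. These are the remaining scheduled safety assessments, the follow-up contact where one is scheduled, and the outcomes of open events.
- These data enter the safety listings and tables.

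This concerns only which data are recorded. What termination should otherwise stop is for the sponsor to decide. The cost is one sentence, no new procedure, and at most a few visits or remote calls that are already planned.

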9.5 Dose adjustment

If the study drug is associated with adverse effects that are a cause for concern, the study can be paused and the dose reduced before further experiments are completed. The study's Principal Investigator will be responsible for this decision and will take into account the incidence of adverse effects, their severity and other relevant factors. If necessary, the sample size of the study may be increased to ensure that the planned number of subjects receive both formulations at the same dose.

10. STATISTICS AND DATA ANALYSIS

10.1 Power analysis

As the means are unknown, we base the power calculation on minimum detectable difference assuming the AUC coefficient of variation in CBD is 50% (Taylor et al. 2018(8)). Since there is no carry-over effect in the study, an appropriate analysis of continuous data from a two-period, two-intervention cross-over trial is a paired t-test (29). For the primary outcome, the bioavailability of lipid versus standard formulation in the fasted state, a paired t-test with n=12 has 80% power, at alpha=0.05 (2 tailed) to detect a 44.5% difference in means.

Previous studies demonstrated increased bioavailability with lipid formulations of 7x(19). The study is adequately powered to demonstrate these differences. This sample size and design satisfies EMA recommendations for design and minimum sample size (n=12) in pharmacokinetic studies for comparing formulations.

10.2 Planned recruitment

The study requires 12 complete datasets. With an expected drop-out rate of 15%, we expect to recruit 14 participants.

10.3 Statistical analysis plan

Pharmacokinetics parameters

Pharmacokinetic parameters will be summarized descriptively. Continuous outcomes will be reported as means with standard deviation. Categorical outcomes will be reported as frequencies. Individual participant's pharmacokinetic data may also be presented in tables and graphs. The plasma concentration-time data will be subject to non-compartmental pharmacokinetic analysis using appropriate computer software applications. Linear and/or log-linear plots will be presented. To assess bioavailability between the formulations, log transformed AUC, C_{max} observations will be entered into a linear mixed model to account for the repeated measures and between subject conditions. Linear contrasts representing the difference between conditions will be expressed as ratio of geometric means along with 95% CI and inference based on $p < 0.05$. Planned analysis will be per protocol.

Protocol violations

All protocol violations, including inclusion/exclusion criteria violations and violations during the trial, will be listed, even if they are believed not to influence any of the results.

Demographics

For all participants, descriptive statistics of demographic (e.g., sex, age, BMI, and other baseline characteristics) will be presented by overall.

Safety measures

Summary tables showing vital signs e.g., body temperature, respiratory rate, pulse rate, and SBP and DBP will be provided at each study time point and changes from baseline.

Individual physical examination will be listed and summarised at each study time point. Important Medical Event, drug, pregnancy test results during the study will be listed.

Visual Analogue Scales & Drug Effects Questionnaire (DEQ-5)

A summary table of DEQ-5 will be summarised descriptively.

Laboratory results

Laboratory parameters including haematology, blood chemistry, and urinalysis will be listed accompanied by an indication if the parameter is outside the reference range. A summary of all data outside the reference range of the clinical laboratory will be provided. Clinical laboratory data will be presented descriptively, where applicable.

Adverse events

A listing of all individual AEs, AR, UAR, SAE, SAR, and SUSAR will be provided. Summary tables of TEAEs will be presented by system organ class based on the MedDRA terminology list (preferred terms): 1 containing the number of TEAEs (frequency of occurrence, number of participants/patients experiencing the event) by treatment and 1 containing the number of drug related TEAEs (frequency of occurrence, number of participants/patients experiencing the event) per treatment. Additional tables of total counts by treatment and relationship and by treatment and severity will be given.

The final statistical analysis plan will be in place prior to study database lock.

11. TRIAL STEERING, DATA MONITORING AND ETHICS MONITORING COMMITTEES

This is a small pharmacokinetic study with a short duration and short follow-up. Safety and pharmacovigilance are important components of the study but costs of running these committees have to offset against the benefit in such a small trial, and also the minimal expected risk from previous published data where cannabidiol has been used in healthy participants and patients. Therefore, there will be no data monitoring or trial steering committees for this study.

12. DIRECT ACCESS TO SOURCE DATA AND DOCUMENTS

The Investigators will permit trial-related monitoring, audits, REC review, and regulatory inspections by providing the Sponsors, Regulators and REC direct access to source data and other documents (e.g. participants' case sheets, blood test reports).

13. ETHICS AND REGULATORY APPROVALS

The trial will be conducted in compliance with the principles of the Declaration of Helsinki (1996), the principles of GCP and in accordance with all applicable regulatory requirements including but not limited to the Research Governance Framework and the Medicines for Human Use (Clinical Trial) Regulations 2004, as amended in 2006 and any subsequent amendments.

This protocol and related documents will be submitted for review to Health Research Authority (HRA), Research Ethics Committee (REC), and to the Medicines and Healthcare products Regulatory Agency (MHRA) for Clinical Trial Authorisation.

The Chief Investigator will submit a final report at conclusion of the trial to the KHP-CTO (on behalf of the Sponsor) and the REC within the timelines defined in the Regulations. The KHP-CTO or delegate will upload the final report to EudraCT on behalf of the Sponsor.

14. QUALITY ASSURANCE

This is a small pharmacokinetic study with a short duration and short follow-up where the majority of outcome data will not be available until after laboratory analysis. The benefits of data audit are therefore limited. Data will be made available for inspection and monitoring by relevant authorities on request. Monitoring of this trial will be to ensure compliance with Good Clinical Practice and scientific integrity will be managed and oversight retained, by the KHP-CTO Quality Team.

15. DATA HANDLING AND MANAGEMENT

The study will adhere to KCL's policy on data management, security and sharing. Participants will provide mobile phone numbers so that we can contact them during the study. If a participant requests, they will be contacted with the study outcome.

The Chief Investigator will act as custodian for the study data and all participant data will be pseudo-anonymised. Data will be collected using source data questionnaires (pen and paper). Each study participant will be given a study ID. Source documents will be named with this ID. The source documents will be kept in locked cabinets. Study data will be transcribed to the Elsevier MACRO EDC system.

All trial data will be stored in line with the Medicines for Human Use (Clinical Trials) Amended Regulations 2006 and the Data Protection Act and archived in line with the Medicines for Human Use (Clinical Trials) Amended Regulations 2006 as defined in the Kings Health Partners Clinical Trials Office Archiving Standard Operating Procedure (SOP).

Research data will be stored for a minimum of 10 years following the completion of the study. Case report forms will be scanned so that they can be stored electronically along with other data from the study. We plan to store the data on King's College London Research Data Management system.

Access to the final trial dataset

The trial steering group will have access to the final dataset of the trial. The dataset will also be made available to the study investigators, and the trial statistician.

